8.2 Regulatory status of the drug

Mepolizumab is currently licensed in the UK for the treatment of severe refractory eosinophilic asthma and has been NICE approved for patients who have adhered to an optimised standard treatment plan.

8.3 Product Characteristics

The Summary of Product Characteristics (SmPC) will be used to obtain information on how to use the medicine and to assess expectedness of events (known as the reference safety information). The SmPC will be provided in the Investigator and Pharmacy Site Files. A new SmPC will be used from 01 March 2024 to reflect the new constitution of the IMP from this date (Nucala 100 mg solution for injection in pre-filled syringe, date of revision of text 23 May 2023).

8.4 Dosage and excipients

Dosing will be undertaken every four weeks (+/- 7 days) over 48 weeks (12 doses in total), each consisting of 100mg of mepolizumab or placebo, administered subcutaneously. Participants are required to complete the scheduled clinic visits within the specified time windows in order to maintain sufficient intervals between doses. Trial medication can only be administered at the Respiratory BRC. The participant will return on an outpatient basis following their initial hospitalisation every four weeks to receive their scheduled dose and undertake trial assessments. For participants who do not receive dosing during their index hospitalisation, the first injection must occur within seven days of discharge. The participant's time in the trial begins at randomisation.

Scheduled doses can be delayed by up to four weeks. The exception will be if dosing is delayed due to an exacerbation resulting in hospitalisation, where there will be no limit on the length of delay, and the next dose will be administered at the next due date or as soon as possible afterwards to allow the participant to recover. A delay will then be carried through to all their subsequent study visits. If the participant misses a dose, it will be recorded in the medical notes and the next scheduled dose will be administered. Participants will be allowed to miss one dose of the study drug only, or they will be discontinued from the trial treatment. Dosing completed outside of the seven-day window will be recorded as a protocol deviation.

8.4.1 Truncated follow-up

Participants consented to the truncated follow-up phase of the study will follow the dosing regimen of one dose every 4 weeks (± 7 days) for at least 20 weeks (minimum of 6 doses with first dose administered at baseline); however, the number of doses will be dependent on when they consented to the study i.e. patients consented earlier will receive more. The method of dosage and blinding procedures will remain the same.

Due to IMP expiry dates and availability of replacement stock, any doses administered from 01 March 2024 will be with IMP or matched placebo solution for injection in a pre-filled syringe.

8.5 Dosage modifications

The dosing regimen in this eosinophilic COPD patient population is as per the licensed indication (severe refractory eosinophilic asthma). In the two clinical studies undertaken using mepolizumab in COPD patients, the safety profile of the drug was in line with the severe refractory eosinophilic asthmatic population. There will be no dose modification during the trial (see Section 8.10 for non-IMP medication changes). No dose adjustments are required for elderly patients.

If a participant has an anaphylactic reaction to the drug or placebo, they will discontinue from trial treatment and be withdrawn from the trial. If the participant is willing, and where appropriate, they will be contacted at their 48 week/Final Follow-up time point to collect information on any additional exacerbations since discontinuation. If the study treatment is stopped due to a clinical reason, such as an allergic reaction, IMP will not be restarted in the same participant.

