7.7.3 Visits 5, 6, 8, 9, 11, 12 (Weeks 16, 20, 28, 32, 40, 44; each visit \pm 7 days) – Dosing only

The following procedures will be performed:

- Review concomitant medication
- Safety & tolerability (AEs; SAEs, Vital signs, Clinical assessments and investigations)
- Urine pregnancy test (if applicable)
- Dosing (see section 8.4).

7.7.4 Visit 13/Final Follow-up (Week 48 ± 7 days) – Final Follow-up (no dosing)

The following procedures will be performed on all participants who completed the trial treatment schedule. Those participants who discontinued treatment prior to visit 12 but remain in the trial will be invited to hospital to attend this final visit.

- Review concomitant medication
- Safety & tolerability (AEs; SAEs, Vital signs, Clinical assessments and investigations)
- Urine pregnancy test (if applicable)
- Outcome measures
 - Quality of Life /Symptoms Assessments (eMRC; SGRO; CAT; WEMWBS; LCADL)
 - Physiological Measures (SPPB; handgrip strength)
 - Inflammatory markers (serum eosinophil count; sputum* eosinophil count)
- Exploratory measures
 - Biomarkers (Sputum* inflammatory differential; sputum* sample: microbiome, systemic inflammation; blood sample: Trop I, BNP, FBC, serum, plasma; urine sample)
 - Muscle wasting (quadriceps ultrasound)
 - Immunophenotyping & Microbiology (Blood: RNA; Sputum*: RNA, Protein multiplex, immunology, microbiology; Urine: lipoproteomics, protein multiplex)

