7.8 Withdrawal criteria

Specified criteria for discontinuation of trial treatment will be for participants that miss more than one dose of the trial treatment or who delay a dose for >4 weeks. The only exception will be when this delay is due to a COPD exacerbation resulting in hospitalisation, in which instance the next dose will be administered at the next due date or as soon as possible afterwards to allow the participant to recover.

Every effort should be made by the research team to keep the participants in the trial. However, participants have the right to withdraw their consent to take part in the trial at any time without having to give a reason and this will not affect their future care. Withdrawal of consent details and reasons (if known) should be recorded on the CRF and in the medical notes.

The investigator may discontinue treatment of a participant at any time if they are not compliant with the trial protocol or to protect the participant's safety and well-being after consultation with the CI. The IMP may also be discontinued in the case of an adverse event which the investigator considers sufficient to jeopardise the safety of the participant. Participants who want to discontinue trial treatment should be encouraged to remain in the trial and

to continue to be followed-up as per the protocol or as per routine care. Participants who discontinue treatment, for whatever reason, will be asked for their consent to continue collecting data, as a minimum this must include data on hospital admissions and deaths for the remainder of the trial (48 weeks) in order to answer the primary outcome. Those declining this will be withdrawn from the trial (thus withdrawing their consent).

Every effort should be made to keep the participant in the trial to collect important efficacy and safety data. Additionally, there are a number of trial assessments (e.g. Quality of Life measures/Symptom Assessments) that may be collected over the telephone if the participant agrees to be contacted. Withdrawals from the trial should be discussed with the CI or their deputy and the Trial Manager. If a participant has withdrawn/discontinued from the trial for any reason, then his/her screening and trial ID number(s) cannot be issued to another participant.

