10.3.2 Primary outcome analysis

The main approach to primary analyses will be intention-to-treat (ITT), where the ITT population consist of all randomised participants. The primary analysis will fit the Cox proportional hazard model for the primary outcome of the time to re-hospitalisation or death (any cause) as the dependent variable, treatment group as an explanatory factor and baseline MRC dyspnoea score (≤ 3 , > 3) and past hospitalisation in the previous 12 months ($(0, \geq 1)$) (Stratification factors). This analysis will be accompanied by Kaplan-Meier survival curves alongside with log rank test to compare the survival rate between the two groups. A hazard ratio (HR) of the mepolizumab relative to placebo, with their associated 95% confidence interval and p-values will be reported. A p-value ≤ 0.05 will be considered as significant difference. Time until event (re-hospitalisation or death from any cause) will be measured in days from randomisation until re-hospitalisation, death or 12-month follow-up assessment, whichever happens first. Participants with no event (no re-hospitalisation or alive) assessed during follow-up visits will be censored at the last assessment date free from event. Participants who do not complete the 12-month follow-up will be included in the primary analysis; those without a recorded event will be censored. Participants who withdraw from the trial will be censored at the date of withdrawal and participants lost to follow up will be censored at the date last assessment.

Proportional hazard assumption for the Cox proportional hazard model will be checked using the statistical tests and graphical diagnostics based on the Schoenfeld residuals.

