10.7 Participant population

The primary analysis for each efficacy outcome will be by 'intention to treat' analysis; all the participants randomised in to the trial (regardless of whether they received trial drug) will be analysed in their allocated group. Outcome data obtained from all participants will be included in the data analysis. The primary analysis of safety outcomes will be analysed using the safety population. The safety population will be comprised of the all individuals that received at least one injection of either the active dose or the placebo, with individuals that received any injections of the active dose being in the mepolizumab arm.

Some of the secondary outcomes i.e. number of hospital readmissions and number of moderate exacerbations over 48 weeks, will be analysed on the per-protocol population where patients will be included in the analysis if they have a received a minimum duration of trial treatment of 24 weeks.

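### Section 8.5 withdraws a participant with anaphylaxis from the trial, whereas section 7.8 keeps consenting treatment discontinuers in follow-up, so later primary events would be censored

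*Protocol*

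**What the plan says.** Protocol section 8.5 deals with anaphylaxis to drug or placebo. Of such participants it says "they will discontinue from trial treatment and be withdrawn from the trial". No consent step is attached to the withdrawal. If the participant is willing, and where it is suitable, they are then "contacted at their 48 week/Final Follow-up time point to collect information on any additional exacerbations since discontinuation".

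Section 7.8 sets the general rule: "Participants who discontinue treatment, for whatever reason, will be asked for their consent to continue collecting data", and "as a minimum this must include data on hospital admissions and deaths for the remainder of the trial (48 weeks"), which the section ties to answering the primary outcome. Withdrawal from the trial follows only from refusal: "Those declining this will be withdrawn from the trial (thus withdrawing their consent"). The section makes no exception for anaphylaxis.

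Section 7.7.4 adds, on the final visit: "Those participants who discontinued treatment prior to visit 12 but remain in the trial will be invited to hospital to attend this final visit".

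On the analysis side, section 10.3.2 says "Participants who withdraw from the trial will be censored at the date of withdrawal", and SAP section 6.4.1 repeats this. Section 10.7 describes the intention-to-treat analysis and says "Outcome data obtained from all participants will be included in the data analysis". The SAP does not mention the anaphylaxis rule, so the conflict sits in the protocol and reaches the analysis through the censoring rule.

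**The concern.** Section 8.5 merges two decisions that section 7.8 keeps apart: stopping the injections and leaving the trial. A site cannot follow both sections for a participant who has a reaction and is willing to be followed.

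If the site follows 8.5, primary-outcome follow-up stops at withdrawal for a reason linked to the injection. If reactions are more common on one arm, so is the censoring, and a person who has just reacted may not have the same prognosis as those still at risk. The Cox model assumes otherwise. SAP section 6.4.3 plans no sensitivity analysis of the primary outcome, so nothing in the plan would show the effect.

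There is also an anomaly. Under section 7.11, a participant who cannot be contacted is still followed through hospital records for hospitalisations and death. A cooperative participant withdrawn under 8.5 is promised less.

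**Working it through.** **The two rules side by side, for a participant willing to stay**

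| Question | Under 8.5 | Under 7.8 |
|---|---|---|
| Status in the trial | Withdrawn, no consent step | Stays unless they decline |
| Data afterwards | One optional contact about exacerbations | At least admissions and deaths |
| Final visit (7.7.4) | Not invited, as no longer in the trial | Invited |
| Primary analysis (10.3.2; SAP 6.4.1) | Censored at withdrawal | At risk until an event or the last event-free assessment |

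The primary endpoint (3.3.1) is all-cause readmission or death. The 8.5 contact names neither component. Even if it brought a COPD admission to light, censoring at withdrawal would exclude that event. The same holds for a later death recorded on the form described in section 9.4. SAE reporting does not fill the gap for readmissions, because section 9.1 exempts clinical outcomes needing hospital admission unless the investigator relates them to the study drug.

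**Size**

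Inputs from protocol sections 10.1 and 7.3: 65% placebo event risk by 48 weeks, hazard ratio 0.6, power 0.8, alpha 0.05 (taken as two-sided), 226 participants inflated to 238, 1:1 allocation.

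1. The plan's own figure. Mepolizumab event risk = 1 − 0.35^0.6 = 0.467. Mean risk = (0.65 + 0.467)/2 = 0.559. Freedman's formula gives [(1 + 0.6)/(1 − 0.6)]² × (1.960 + 0.842)² = 16 × 7.85, or 126 events. Then 126/0.559 = 225.5, rounded up to 226, and 226/0.95 = 237.9, rounded up to 238. Both stated figures reproduce.
2. Participants affected. The documents give no anaphylaxis rate, so 0 to 2% is an assumption. Per arm, 238/2 = 119, and 119 × 0.02 = 2.4. The range is 0 to about 2 people.
3. Events lost, worst case. Suppose every reaction occurs at day 0 and the full 48-week risk is lost: 2.4 × 0.467 = 1.1 events.
4. Power. With 226 participants the expected number of events is 226 × 0.5587 = 126.3. For k mepolizumab participants censored at day 0, D = 126.3 − 0.467k and power = Φ(√D × 0.4/1.6 − 1.96).

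| k withdrawn | Expected events | Power |
|---|---|---|
| 0 | 126.3 | 80.2% |
| 1 | 125.8 | 80.1% |
| 3 | 124.9 | 79.8% |
| 5 | 123.9 | 79.5% |
| 10 | 121.6 | 78.7% |

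**The case against.** Three stronger readings are tempting, and the documents do not support them.

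- **Safety data are cut off.** They are not. Section 9.2 carries SAE and SUSAR reporting to 28 days after early cessation for every early discontinuer. Section 9.8 follows a participant after an adverse reaction as long as clinical need dictates, records adverse reactions to four weeks after the last dose, and keeps SUSAR reporting open until resolution. Section 9.4 provides a form for deaths beyond 28 days. Section 2.1 promises to monitor and analyse anaphylaxis, and the reaction itself is recorded. What withdrawal removes is the later scheduled visits and the final visit.
- **No admissions would be learned of.** Section 1 defines a severe exacerbation by unscheduled hospitalisation, so the 8.5 contact may pick up COPD admissions. Admissions for other causes and deaths are not asked for.
- **Intention to treat is broken.** The participant stays in the allocated arm and contributes time up to censoring. The fair criticism is possibly informative censoring.

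It can also be said that the numbers are trivial and the 1.1 events too high. That is right. The endpoint is time to first event, so a reaction after a readmission loses nothing, a reaction after a later dose loses less than the full risk, and a reaction that itself causes readmission is already an event. Participants on truncated follow-up have at most 44 weeks to lose.

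Nor does 7.8 promise follow-up to everyone who stops treatment; it depends on consent. None of this removes the contradiction for a participant who would consent.

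**Conclusion.** Sections 8.5 and 7.8 give incompatible instructions about follow-up after anaphylaxis. Following 8.5 as written would exclude a willing participant's later primary events through censoring that may depend on treatment.

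The effect on the result is likely to be very small: 0 to about 2 people and at most about one lost event, resting on an assumed rate of 0 to 2% and on worst-case timing. Three such withdrawals would move power only from 80.2% to 79.8%. The reason to act is that the loss is avoidable and the correction almost free, not that power is threatened. The rule for stopping treatment is outside this point.

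**What to change.** Reconcile 8.5 with 7.8 by separating stopping treatment from leaving follow-up:

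- In 8.5, remove the automatic withdrawal from the trial and leave the treatment-stopping part as it stands.
- Replace the optional exacerbation contact with the consent-based collection in 7.8: admissions and deaths to week 48, or to the scheduled Final Follow-up for truncated participants.
- Invite these participants to Visit 13 under 7.7.4, and treat as withdrawn only those who decline. Section 7.11 is not a substitute, since its record-based follow-up is written for those lost to follow-up.
- In SAP section 6.4.1, state before database lock that any participant already handled under 8.5 who consents to data collection is not censored at the date treatment stopped.

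The cost is one sentence in each document, using procedures that already exist. Timing favours the SAP change: the current protocol version is dated 10 May 2024 (Appendix 3) and section 8.1 has dosing running to June 2024, so an amended 8.5 could govern few remaining doses. SAP section 1 allows changes until database lock.

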8.6 Packaging and labelling

GlaxoSmithKline (GSK) are providing commercially produced mepolizumab, and matched placebo for doses from 01 March 2024, for use in the COPD-HELP trial from GSK, Parma Italy. GSK will arrange for delivery of mepolizumab and matched placebo, where applicable, to a third-party company, who will be responsible for labelling in line with Annex 13 of the EU Guidelines for Good Manufacturing Practice and QP release of the IMP. The third-party company will then arrange for delivery of the labelled mepolizumab and matched placebo, where applicable, to the recruiting site at regular intervals according to trial requirements communicated by Pharmacy. Allocation of trial medication (mepolizumab or placebo) will be managed by Sealed Envelope (web-based randomisation system). The mepolizumab or placebo will be prepared and a blinded label applied to the syringe by unblinded trial personnel (see section 7.3-7.5 on Blinding and Randomisation). All information will be documented on an unblinded participant IMP/placebo preparation worksheet by the unblinded trial personnel, the pharmacist will maintain unblinded accountability logs.

8.7 Drug supply, storage, dispensing and returns

The trial funder, GlaxoSmithKline (GSK), will supply the mepolizumab free of charge for the duration of the trial; they will also supply the matched placebo to the pre-filled syringes used for dosing from the 01 March 2024. Mepolizumab and matched placebo, where applicable, will be provided as open-label product to unblinded

pharmacy and trial staff. Unblinded staff will be responsible for the receipt and storage. GSK will supply sufficient mepolizumab and matched placebo, where applicable, to treat all participants. The participating centre (University Hospitals of Leicester, UHL) will be allocated an initial supply of trial mepolizumab at site activation. Stock levels at UHL pharmacy will be monitored by the clinical trials pharmacy team. When mepolizumab supplies reach a pre-determined level then Pharmacy will request further supply of mepolizumab. Placebo will be prepared from clinical stock of saline at Glenfield Hospital up until 29 February 2024, whereby from 01 March 2024, the study will use the solution for injection in pre-filled syringe with pre-filled matched placebo syringes.

At site the mepolizumab and matched placebo, where applicable, will be stored between 2-8°C. Storage of mepolizumab and matched placebo, where applicable, at site will be in a secure location, in a temperature-controlled environment, with a temperature log maintained for each working day. Any temperature excursions must be reported to the coordinating centre as soon as they are identified.

The local site Clinical Trials Pharmacist is responsible for ensuring mepolizumab/placebo accountability, including reconciliation of mepolizumab/placebo and maintenance of mepolizumab/placebo records, throughout the course of the study in accordance with UK regulatory requirements. Mepolizumab/placebo may be dispensed only by specifically authorised personnel. Responsibility for certain tasks related to the management of the mepolizumab/placebo will be delegated to the site pharmacy clinical trials staff and other members of the site trial team.

Mepolizumab/placebo is supplied for use in the COPD-HELP Trial and must only be prescribed for participants randomised into this trial. Prescriptions should be made available for review as source data, if required.

Where a vial or pre-filled syringe of mepolizumab has been allocated or has been reconstituted but not administered to the participant, if a full cold chain (documentation by the unblinded members of the research team) of time into fridge after leaving pharmacy and time returned to pharmacy is present, the pharmacist who receives the returned stock will seek permission from the sponsor to return the IMP back to stock, otherwise stock will be returned to Pharmacy and placed in quarantine until permission to destroy is received from the Sponsor.

8.8 Preparation of Investigational Medicinal Product (IMP)

Mepolizumab, as a powder, is supplied in lyophilised white powder requiring reconstitution prior to administration, used for dosing visits up to and including 29 February 2024. It is preferable to confirm the participant will be attending for their visit before writing up the prescription to avoid wastage. A mechanical reconstitution device (swirler) is required. Reconstituted mepolizumab must be discarded within eight hours if not administered. Detailed instructions for preparation and reconstitution of mepolizumab or the placebo are provided in the Pharmacy Management Manual. For dosing visits from 01 March 2024, mepolizumab will be in the form of a solution for injection in a pre-filled syringe. The pre-filled syringe will be removed from the refrigerator and administered within eight hours once the pack has been opened. The pack should be discarded if not administered within eight hours.

Dispensing will be recorded on the appropriate trial specific accountability forms. Mepolizumab must not be used for any other purpose than the present study. Mepolizumab/placebo that has been dispensed from pharmacy and prepared for administration to a participant must not be re-dispensed or re-issued to a different participant. Unused mepolizumab and matched placebo, where applicable, at the end of the trial or which has expired will be returned to the local pharmacy to be recorded and final accountability performed.

Further details regarding the mepolizumab will be provided in the Pharmacy Management Manual.

